8.8.3 Treatment of dyslipidemia

Treatments for dyslipidemia, such as statins, are permitted. Any change and reason for change should be recorded on the patients' eCRF. Doses of medications for dyslipidemia should be stable for at least 6 weeks prior to screening visit. Anti-IL-6 drugs, including sarilumab are known to increase serum total cholesterol and this effect will be closely monitored during the study. If, during the treatment period of this study, patients are found to have significant increase in cholesterol levels, or other lipid abnormalities, then cholesterol lowering therapy with statins, or other treatment(s) for dyslipidemia, per American College of Cardiology (ACC)/American Heart Association (AHA) guideline or European Society of Cardiology (ESC)/the European Atherosclerosis Society (EAS) guidelines or local guidelines, should be initiated or the dose adjusted. A referral to a specialist should be considered when dyslipidemia is difficult to manage, such as patients who have elevated low-density lipoprotein (LDL) in spite of being treated with maximum dose of statins.

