10.7.7 Management of dyslipidemia

Patients treated with tocilizumab have been observed to have increased elevations of all lipid parameters, including LDL cholesterol. A similar finding has been observed for sarilumab. The potential cardiovascular effect of the lipid elevations, including LDL levels with antiIL-6R antagonists is unknown.

Patients who are found to have dyslipidemia during the course of the study should be treated according to the American College of Cardiology (ACC)/American Heart Association (AHA) guideline or European Society of Cardiology (ESC)/the European Atherosclerosis Society (EAS) guidelines or applicable local guideline.

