
• Increase in BP of >10% such that the systolic BP exceeds 120 mmHg or the diastolic BP exceeds 85 mmHg without a change in medication OR• An increase in anti-hypertensive medication accompanied by stability or no significant change in both the systolic and diastolic BP 
d. Worsening of hypertension despite treatment:
 
• Increase in BP of >10% such that the systolic BP exceeds 120 mmHg or the diastolic BP exceeds 85 mmHg AND an increase in medication

4. Lipid metabolism (low-density lipoprotein [LDL] compared to baseline)
 
a. Improvement in lipids:
 
• Decrease in LDL concentration >10% of baseline toward the target range without medication increase OR• Decrease in medication without an increase in LDL of >10% or LDL remains within target range 
b. No significant change in LDL:
 
• LDL within 10% of baseline or within the target range for patient AND no change in medication OR• Increase in LDL > 10% with a decrease in medication OR• Improvement in LDL of > 10% with an increase in medication 
c. Worsening of LDL or medication status:
 
• Increase in LDL of >10% to above target range without a change in medication OR• Increase in medication with <10% change in LDL 
d. Worsening of LDL despite treatment:
 
• Increase in LDL of >10% AND an increase in medication

5. Bone Mineral Density (compared to baseline)
 
a. Improvement – increase in BMD by >3%
 
b. No significant change (BMD between -3% and +3%)
 
c. Deterioration - decrease in BMD (BMD decrease by >3%)
 
% refers to total BMD in gms/cm²

6. Glucocorticoid-induced myopathy
 
a. No steroid myopathy
 
b. Mild steroid myopathy (weakness WITHOUT functional limitation)
 
c. Moderate steroid myopathy (weakness WITH functional limitation)
 
See Steroid Myopathy definitions, below

7. Skin
 
a. No skin toxicity
 
b. Mild skin toxicity
 
c. Moderate skin toxicity

See Skin definitions, below

8. Neuropsychiatric toxicity
 
a. No neuropsychiatric symptomsb. Mild neuropsychiatric symptomsc. Moderate neuropsychiatric symptoms 
See Neuropsychiatry definitions, below

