Improvement in BP OR decrease in medication	-19	Posterior reversible encephalopathy syndrome
No significant change	0	
Increase in BP OR increase in medication	19	
Increase in BP AND increase in medication	44	
4.Hyperlipidemia		
Decrease in LDL AND decrease in medication	-30	
Decrease in LDL OR decrease in medication	-10	
No significant change	0	
Increase in LDL OR increase in medication	10	
Increase in LDL AND increase in medication	30	
5.Bone Health (BMD)		
Increase in BMD (gain of more than 3%)	-29	Major decrease in bone density
No significant change in BMD (\pm 3%)	0	Insufficiency fracture

Composite GTI	Item weight	Specific List¹
Decrease in BMD (loss of more than 3%)	29	
6.Steroid myopathy		
Moderate weakness to none	-63	Severe steroid myopathy
Moderate to Mild weakness	-54	
Mild weakness to none	-9	
No significant change	0	
None to Mild weakness (without functional limitation)	9	
Mild to Moderate weakness	54	
None to Moderate weakness (with functional limitation)	63	
7.Skin steroid-related Toxicity		
Decrease in Skin Toxicity - Moderate to None	-26	Severe skin toxicity
Decrease in Skin Toxicity - Moderate to Mild	-18	
Decrease in Skin Toxicity - Mild to None	-8	
No significant change	0	
Increase in Skin Toxicity - None to Mild	8	
Increase in Skin Toxicity - Mild to Moderate	18	
Increase in Skin Toxicity - None to Moderate	26	
8.Neuropsychiatric - steroid related symptoms		
Decrease in NP Toxicity - Moderate to None	-74	Psychosis
Decrease in NP Toxicity - Moderate to Mild	-63	GC-induced violence
Decrease in NP Toxicity - Mild to None	-11	Other severe neuropsychiatric symptoms
No significant change	0	
Increase in NP Toxicity - None to Mild	11	
Increase in NP Toxicity - Mild to Moderate	63	
Increase in NP Toxicity - None to Moderate	74	
9.Infection		
No infection	0	Grade IV infection
Oral or vaginal candidiasis or non-complicated zoster (<Grade3)	19	Grade V infection
Grade 3, 4, or 5 infection	93	

¹ Maximum weight is given for specific list events in Blood pressure, Steroid myopathy, Skin toxicity, Neuropsychiatric and Infection domains at each visit. For the rest of domains, specific list events will not affect the corresponding domain specific score.

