2.4.4.1 Analysis of primary and additional efficacy endpoint(s)

The analysis of primary endpoint of sustained remission at Week 52 will be limited to the cohort of patients who had an opportunity to complete the 52-week treatment period (i.e., Week 52 Analysis set).

The proportion of patients achieving sustained remission at Week 52 will be summarized using counts and percentages by the 4 treatment groups. In addition, the treatment effects between the combined sarilumab (group A+B) group and the combined placebo group (Group C+D) will be compared using a Cochran-Mantel-Haenszel (CMH) test stratified by prednisone dose at baseline (<30 mg/day or ≥30 mg/day).

The additional endpoint of sustained remission at Week 24 will be analyzed in the same fashion in the ITT population.

Sensitivity analysis excluding acute phase reactants:

Sensitivity analysis will be performed for the primary endpoint by removing the acute phase reactants (CRP and ESR) from the definition to mitigate against the possibility of biasing the results due to the known PD effect of sarilumab on acute phase reactants.

Patients achieving sustained remission at Week 52 (or Week 24) excluding acute phase reactants is defined by having met all of the following parameters:

- Achievement of disease remission not later than Week 12. **Disease remission** is defined as resolution of signs and symptoms of GCA.
AND
- Absence of disease flare from Week 12 through Week 52 (or Week 24). **Flare** is defined as recurrence of signs and symptoms attributable to active GCA plus an increase in CS dose due to GCA.
AND
- Successful adherence to the prednisone taper from Week 12 through Week 52 (or Week 24).

The sensitivity analysis will be performed in the same fashion as for the primary endpoint. Descriptive statistics (i.e., counts and percentages) will be provided for the three individual components.

Subgroup analyses:

No subgroup analyses will be performed due to the small sample size.

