Appendix I Baseline glucocorticoid toxicity

Approach to calculating the Baseline glucocorticoid toxicity score: Toxicities assigned weighted scores from the Composite Index to establish a baseline glucocorticoid toxicity score

Toxicity Domain		Points
Body Mass Index (BMI)	BMI < 27	0
	BMI > 27 but < 30	21
	BMI > 30	36
Glucose Metabolism	HgbA1c < 5.7	0
	HgbA1c < 5.7 but on medication	32
	Hgb A1c > 5.7	32
	HgbA1c > 5.7 and on medication	44
	Diabetic retinopathy, nephropathy, or neuropathy (count only one)	44
Lipid Metabolism	LDL < target ^a	0
	LDL < target ^a but on medications	10
	LDL > target ^a on no medications	10
	LDL > target ^a on treatment	30
Bone/Tendon	Normal BMD or no known history of osteoporosis	0
	Osteoporosis	29
	Insufficiency fracture secondary to osteoporosis	29
	Osteonecrosis	29
	Tendon rupture while on corticosteroid	29
Glucocorticoid Myopathy	No myopathy	0
	Minor glucocorticoid myopathy	9
	Moderate glucocorticoid myopathy	63
	Severe glucocorticoid myopathy	63
Skin	No skin toxicity	0
	Minor skin toxicity (one or more than one minor skin item)	8
	Moderate skin toxicity (one or more than one moderate skin item)	26
	Severe skin toxicity (one or more than one moderate skin item)	26
Neuropsychiatric	No neuropsychiatric toxicity	0
	Minor (one or more than one minor NP item: insomnia, mania, depression, cognitive)	11
	Moderate (one or more than one moderate NP item: insomnia, mania, depression, cognitive)	74
	Severe (one or more than one severe NP item: insomnia, mania, depression, cognitive)	74
	Psychosis	74
	Glucocorticoid-induced violence	74
Infection	No GTI-relevant infections within the pre-baseline GTI interval of the study	0
	Oral or vaginal candidiasis or non-complicated zoster (<Grade3) within the pre-baseline GTI interval of the study	19

[figure not shown]
	Grade 3 or Grade 4 infection within the pre-baseline GTI interval of the study	93
Ocular	Increased IOP	33
	Posterior subcapsular cataract	33
	Central serous retinopathy	33
Gastrointestinal	GI perf absence of NSAIDs	33
	PUD without H. pylori	33
Endocrine	Adrenal insufficiency	33

a Target range of <70 mg/dL will be used for LDL domain.

Signature Page

efc15068-16-1-9-sap

Approve & eSign

Approve & eSign

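### The GTI lipid domain may count a known sarilumab effect as steroid toxicity, and no supportive CWS or AIS without that domain is planned

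*SAP*

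**What the plan says.** **Scoring.** The GTI is the plan's measure of whether sarilumab spares patients steroid toxicity (SAP Section 1.2.2). In SAP Section 2.1.3.2, Table 4, the Hyperlipidemia domain gives +10 for "Increase in LDL OR increase in medication" and +30 for "Increase in LDL AND increase in medication". Protocol Appendix C supplies the triggers:

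- The lower worsening category includes "Increase in LDL of >10% to above target range without a change in medication". It also includes a medication increase with less than 10% change in LDL.
- The higher worsening category is an LDL rise of more than 10% together with a medication increase.
- An LDL improvement of more than 10% with a medication increase is no significant change, which scores 0.

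SAP Appendix I adds: "Target range of <70 mg/dL will be used for LDL domain".

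**Use.** All nine domains are summed at each visit, then across Weeks 12 and 24 (Week 24 score) or Weeks 12, 24, 40 and 52 (Week 52 score). SAP Section 2.4.4.2 compares CWS and AIS between the combined sarilumab and combined placebo groups by ANCOVA, and gives odds ratios for the dichotomised scores.

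**Drug effect.** Protocol Section 8.8.3: "Anti-IL-6 drugs, including sarilumab are known to increase serum total cholesterol and this effect will be closely monitored during the study". The same section has lipid therapy started or adjusted for significant increases. Protocol Section 10.7.7: "Patients treated with tocilizumab have been observed to have increased elevations of all lipid parameters, including LDL cholesterol", followed by "A similar finding has been observed for sarilumab".

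**Supportive analyses.** SAP Appendix C enters No under supportive analysis for the GTI; domain-level scores are summarised descriptively. For the primary endpoint, SAP Section 2.4.4.1 removes CRP and ESR in a sensitivity analysis, to guard against "biasing the results due to the known PD effect of sarilumab on acute phase reactants".

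**The concern.** The GTI comparison is meant to show what the lower steroid exposure does to steroid toxicity. One of its nine domains also responds to a laboratory change that the protocol attributes to the study drug, and to the treatment that sites are told to give for that change. A sarilumab patient whose LDL rises because of sarilumab collects the same points as a patient whose LDL rises because of prednisone.

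A true steroid-sparing effect could then look smaller than it is in the ANCOVA. In the dichotomised analysis a single +10 takes a patient with no other worsening from a CWS of zero to above zero. In the AIS, +10 at a visit outweighs an improvement of −8 (mild skin toxicity resolved) or −9 (mild myopathy resolved). A reader who sees no difference in CWS could not tell whether steroid toxicity was similar or a lipid effect offset a benefit elsewhere.

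**Working it through.** **1. Confirm that the lipid weight is in the total.** Protocol Section 9.2.1.4 states a maximum composite score of 439. Summing the largest positive weight per domain in SAP Table 4 (BMI, glucose, blood pressure, lipids, bone, myopathy, skin, neuropsychiatric, infection):

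36 + 44 + 44 + 30 + 29 + 63 + 26 + 74 + 93 = 439.

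The stated figure reproduces exactly with the lipid weight of 30 included. Without it the maximum is 439 − 30 = 409, so lipids are 30/439 = 6.8% of the per-visit maximum.

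**2. Contribution per patient.** Points = weight per visit × number of visits summed. This assumes that each visit is scored against baseline, as protocol Appendix C has it.

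| Pattern | Week 24 (2 visits) | Week 52 (4 visits) |
|---|---|---|
| LDL improves by >10% with added medication | 0 | 0 |
| Lasting LDL rise, no medication change | 2 × 10 = 20 | 4 × 10 = 40 |
| LDL raised despite increased medication at every visit | 2 × 30 = 60 | 4 × 30 = 120 |

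The last row is a ceiling. For scale, new mild skin toxicity is +8 and new mild neuropsychiatric toxicity is +11 at a visit.

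SAP Section 2.1.3.2 also describes the CWS as adding new toxicities. If a lasting rise were counted only when new, it would add 10 once, not 20 or 40.

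**3. Shift in the group mean.** The documents give no rate of LDL rise, so this is an assumption shown over a range. Let the excess share of sarilumab patients scoring at each visit be 10% to 40%. Mean shift = share × weight × visits.

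- At +10: 0.1 × 10 × 2 = 2 to 0.4 × 10 × 2 = 8 points at Week 24; 4 to 16 at Week 52.
- At +30: 6 to 24 points at Week 24; 12 to 48 at Week 52.

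**4. Dichotomised CWS.** Suppose a share q would have CWS above zero from the other eight domains, and an independent excess share f of sarilumab patients scores on lipids. The sarilumab share above zero becomes 1 − (1 − q)(1 − f). With assumed f of 20% to 40%:

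- q = 30% becomes 44% to 58%.
- q = 50% becomes 60% to 70%.
- q = 70% becomes 76% to 82%.

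**5. Direction.** Every lipid point caused by the drug raises CWS and AIS in the sarilumab group, and a lower score is the favourable one. The bias runs against sarilumab.

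**The case against.** The case for leaving the plan alone has real substance.

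- **The lipid effect will be visible.** Domain scores are tabulated by group and visit, and SAP Section 2.4.5.3 covers LDL by visit and time to LDL elevation. Protocol Section 9.2.1.4 presents domain reporting as the way to see one domain offset another. This stands, but group-level domain summaries cannot produce the adjusted CWS or AIS difference, or the odds ratios, without lipids. Those need recalculation per patient.
- **The CRP/ESR analysis is not an exact parallel.** There the drug effect could flatter sarilumab; here it works against it. That stands. The precedent shows that the plan accepts the principle of removing a component the drug affects. It does not oblige the plan to do so here.
- **Dropping one domain is selective.** Protocol Section 10.7.1 says infections were the most commonly reported treatment-emergent events in sarilumab studies, and the infection domain carries +19 or +93. This stands, and it is why the eight-domain score can only be supportive.
- **The stakes are limited.** The GTI was outside the protocol's testing hierarchy, all p-values are nominal, and the Week 52 GTI analysis uses 36 patients.

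A reader might also infer more than the documents support:

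- *Every added lipid drug counts as toxicity.* It does not: the score is 0, +10 or +30 depending on the LDL response.
- *The bias is established and large.* The documents call the effect known, but give no LDL size or rate, and do not say that it is direct.
- *A patient whose only change is LDL is classed as worsened.* As printed, SAP Section 2.4.4.2 labels a CWS above zero as not worsening and zero or below as worsening. The labels appear reversed, since CWS can only rise with toxicity, but the text does not classify that patient as worsened.

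**Conclusion.** The point holds as a gap in interpretation. The lipid domain can score a known sarilumab effect, and the treatment given for it, as glucocorticoid toxicity, and the plan has no version of CWS or AIS that leaves it out. The scores may be biased against sarilumab by an unknown amount. Per patient, a lasting LDL rise is worth 20 points at Week 24 and 40 at Week 52, provided that each visit is scored against baseline. The 60 and 120 ceilings also need LDL to stay raised despite increased medication at every visit. The group-level shifts rest on assumed rates.

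Nothing here suggests a false claim of benefit or a type I error problem. It does not make the nine-domain result invalid either. The consequence is that a null or small GTI difference would be hard to read.

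**What to change.** Add one prespecified supportive analysis to SAP Section 2.4.4.2 and to SAP Appendix C: CWS and AIS at Weeks 24 and 52 recomputed on the eight domains without Hyperlipidemia, with the lipid item also removed from the baseline toxicity score used as a covariate. Apply the same ANCOVA and odds ratios, with the same visit-scoring rule as the main analysis. Before running the odds ratios, correct the worsening and not-worsening labels in SAP Section 2.4.4.2. Keep the nine-domain score as the main result.

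The cost is one extra run on data already derived, with no new collection. The downside is that the eight-domain score departs from the published instrument and does not deal with other domains that a drug effect could touch, such as infection. It should be labelled supportive only. Specifying it before database lock avoids a post hoc explanation.

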2.1.4 Safety endpoints

The safety analysis will be based on the reported adverse events (AEs), serious AEs (SAEs) and adverse events of special interest (AESIs) including but not limited to neutropenia, thrombocytopenia, elevations in hepatic enzymes leading to permanent discontinuation and

tuberculosis, and other opportunistic infections. Other safety information, such as clinical laboratory data and vital signs will also be assessed.

Observation period

The observation period will be divided into 4 epochs:

- The **screening** epoch is defined as the time from the signed informed consent date up to the time prior to first dose of SC IMP.
- The **treatment** epoch is defined as the time from the first dose of the IMP to the last dose of the SC IMP in the DB period +13 days.
- The **residual treatment** epoch is defined as the time from the end of TREATMENT epoch to the last dose of the SC IMP +60 days.

The **post-treatment** epoch is defined as the time after the last dose of SC IMP +60 days. The rationale of having “last dose of SC IMP +60 days” as the end of follow-up epoch is to capture the events observed within an approximately 5 half-lives of the last sarilumab SC IMP.

The treatment-emergent adverse event (TEAE) period includes both **treatment** and **residual treatment** epochs.

2.1.4.1 Adverse events variables

Adverse event observation period

- Pre-treatment AEs are AEs that developed or worsened or became serious from the signed informed consent date up to first administration of SC IMP
- TEAEs are AEs that developed or worsened or became serious during the TEAE period
- Post-treatment AEs are AEs that developed or worsened or became serious during the post-treatment period

All AEs (including SAEs and AESIs) will be coded to a “LLT”, “PT”, “HLT”, “HLGT”, and associated primary “SOC” using the version of MedDRA currently in effect at Sanofi at the time of database lock.

The occurrence of AEs (including SAEs and AESIs) will be recorded from the time of signed informed consent until the end of the study.

Any SAE brought to the attention of the Investigator at any time after the end of the study for the patient and considered by him/her to be caused by the IMP with a reasonable possibility, should be reported to the monitoring team.

Adverse event of special interest (AESI)

Adverse events of special interest will be flagged in the database. The AESIs and its search criteria are listed in [Table 5](#) below:

Table 5 - Protocol defined AESIs and search criteria

AESI flag	Search criteria
Clinically significant infections including: 
 • Opportunistic infections • Tuberculosis • Infections requiring prolonged medication • Infections requiring parenteral treatment 	Reported by the investigators on the AE CRF page with AESI box ticked.
Lab abnormalities including: 
 • ALT increase leading to permanent discontinuation • ANC decrease leading to permanent discontinuation • Thrombocytopenia leading to permanent discontinuation 	
ALT >= 3xULN	
Pregnancy	CRF checkbox: Pregnancy
Overdose	CRF checkbox: Symptomatic Overdose

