4.1 BENEFIT AND RISK ASSESSMENT

The available aggregate nonclinical and clinical data from the sarilumab development program in RA have demonstrated a potent anti-inflammatory effect and significant clinical benefit for patients with active RA via blockade of the IL-6 signaling pathway, which is also thought to play a key role in the pathogenesis of GCA. Therefore, treatment of GCA patients with sarilumab may lead to clinical benefits as observed in patients with active RA. This likely benefit with sarilumab is further supported by the pivotal GiACTA trial (a phase 3 study which evaluated efficacy and safety of tocilizumab in GCA patients [9]) that resulted in the approval of a similar IL-6 inhibitor, tocilizumab, for the treatment of GCA. Because of the similarity of sarilumab to tocilizumab and a study design that mirrors the successful GiACTA trial, it is expected that the current study will demonstrate a similar efficacy for sarilumab in GCA. Sarilumab is already approved for the treatment of rheumatoid arthritis in multiple countries.

Based on the safety profile of sarilumab available to date and other biological DMARDs, important identified risks include serious infections, neutropenia and hypersensitivity reactions; important potential risks to be considered with sarilumab administration, consistent with this class of therapy, include laboratory abnormalities and the potential clinical consequences, such as thrombocytopenia and the potential risk of bleeding, clinically evident hepatic injury with elevated hepatic transaminases, and lipid abnormalities and potential increased risk of major adverse cardiovascular event (MACE). Other potential important risks include increased risk of malignancy and gastrointestinal perforation. Various risk mitigation strategies are either built into the eligibility criteria (Section 7.1 and Section 7.2) to exclude those with conditions that may jeopardize their safety or into other sections of the protocol (Section 10.4 and Section 10.7) for monitoring and management of certain risks/adverse events (eg, neutropenia, thrombocytopenia, liver transaminase elevation, etc).

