10.5.1.3 Adverse event of special interest

An AE of special interest (AESI) is an AE (serious or nonserious) of scientific and medical concern specific to the Sponsor's product or program, for which ongoing monitoring and immediate notification by the Investigator to the Sponsor is required. Such events may require further investigation in order to characterize and understand them. Adverse events of special interest may be added, modified or removed during a study by protocol amendment.

The following listed events are considered as AESI:

- Pregnancy of a female subject entered in a study as well as pregnancy occurring in a female partner of a male subject entered in a study with IMP; Pregnancy occurring in a female patient entered in the clinical trial or in a female partner of a male patient entered in the clinical trial. It will be qualified as an SAE only if it fulfills one of the seriousness criteria (see [Section 10.5.1.2](#)).
 - In the event of pregnancy in a female participant, IMP should be discontinued.
 - An attempt to follow up of the pregnancy in a female participant or in a female partner of a male participant is made until the outcome has been determined (see [Appendix A](#)).
- Symptomatic overdose (serious or nonserious) with SC IMP.
- An overdose (accidental or intentional) with the SC IMP is an event suspected by the Investigator or spontaneously notified by the patient and defined as at least twice the intended dose during an interval of <11 days (for sarilumab or matching placebo).

Of note, both symptomatic and asymptomatic overdoses have to be reported on a specific AE page. The circumstances (ie, accidental or intentional) should be clearly specified in the verbatim and symptoms, if any, entered on separate AE forms.

- Increase in alanine transaminase (ALT) ≥ 3 x ULN (see the “Increase in ALT” flow diagram in [Appendix L](#)). Clinically significant infections including:
 - Confirmed diagnosis of opportunistic infections based on the Investigator’s assessment with appropriate diagnostic workups and consultations. For any infection from the list of potential opportunistic infections provided in [Appendix M](#), for reporting purpose, even if it is not confirmed to be an opportunistic infection based on the Investigator’s assessment, it should still be reported as AESI.
 - Active/latent TB or initiation of medications for suspected TB.

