10.7.6 Diverticulitis and gastrointestinal perforation

The Investigator should pay particular attention to gastrointestinal symptoms such as, but not limited to, abdominal pain, hemorrhage, or unexplained change in bowel habits with fever to assure that the diagnosis is not missed and that the conditions are managed appropriately to avoid the complication of perforation. If necessary, the patient should be referred to a specialist.

Corticosteroid use or prior history of diverticulitis is known to increase the risk of gastrointestinal perforations. The Investigator should be aware of this potential risk and monitor any sign of diverticulitis.

Gastro-intestinal perforation must be reported as SAE (see [Section 10.5.4](#)). Confirmed diverticulitis or gastrointestinal ulceration should be reported as AEs.

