11.4.3.1 Analysis of adverse event data

Treatment-emergent AEs, treatment-emergent SAEs, TEAEs leading to treatment discontinuation and treatment-emergent AESIs will be summarized for each treatment group based on MedDRA coding of verbatim terms reported by Investigators.

Adverse event incidence tables will present by system organ class (SOC) (sorted by internationally agreed order), high-level group term (HLGT), high level term (HLT) and preferred term (PT) sorted in alphabetical order for each treatment group, the number (n) and percentage (%) of patients experiencing an AE. Multiple occurrences of the same event in the same patient will be counted only once in the tables within a treatment period. The denominator for computation of percentages is the safety population within each treatment group.

Treatment-emergent AESI, by AESI category and PT, will show number (%) of patients overall, sorted by decreasing incidence of PT within each AESI category. The AESIs include, but are not limited to, the following categories and details of the MedDRA coding will be provided in the statistical analysis plan: Neutropenia, thrombocytopenia, infections, hepatic disorders, diverticulitis/GI ulcerations/GI perforations, elevation in lipids, systemic allergic reactions, malignancy, autoimmune or drug-induced lupus like syndrome and demyelinating disorders.

Death: The following deaths summaries will be generated:

- Number (%) of patients who died by study period (TEAE, on-study) summarized on the safety population by treatment received
- Death in nonrandomized patients or randomized and not treated patients
- TEAE leading to death (death as an outcome on the AE CRF page as reported by the Investigator) by primary SOC, HLGT, HLT and PT showing number (%) of patients sorted by internationally agreed order of SOC and alphabetic order of HLGT, HLT, and PT.

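### SAP Table 5 follows the protocol's AESI reporting list but not its ten AESI analysis categories, and SAP 1.6 does not declare this

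*SAP*

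**What the plan says.** Protocol 10.5.1.3 introduces its list with "The following listed events are considered as AESI". It covers pregnancy, symptomatic overdose, ALT of at least 3 x ULN, clinically significant infections, and ALT, neutrophil or platelet abnormalities that lead to permanent discontinuation. These events go to the sponsor within 24 hours (10.5.5).

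Protocol 11.4.3.1, the analysis section, says treatment-emergent AESIs will be tabulated by category and preferred term. It gives an open-ended list of categories: "Neutropenia, thrombocytopenia, infections, hepatic disorders, diverticulitis/GI ulcerations/GI perforations, elevation in lipids, systemic allergic reactions, malignancy, autoimmune or drug-induced lupus like syndrome and demyelinating disorders". It adds that "details of the MedDRA coding will be provided in the statistical analysis plan".

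SAP 2.1.4.1, Table 5, is presented as the protocol-defined AESIs with their search criteria. Its rows are those of protocol 10.5.1.3. The criterion for infections and laboratory abnormalities is "Reported by the investigators on the AE CRF page with AESI box ticked"; pregnancy and overdose come from CRF checkboxes. SAP 2.4.5.1 then builds every AESI display from these criteria: overview, treatment duration, incidence, serious, leading to discontinuation, leading to death, and possibly related.

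Protocol 4.1 says that "important identified risks include serious infections, neutropenia and hypersensitivity reactions", and later that "Other potential important risks include increased risk of malignancy and gastrointestinal perforation".

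**The concern.** The analysis section of the protocol promised grouped tables for ten risk categories and handed the coding to the SAP. A programmer following the SAP as written would produce AESI tables with no category for hypersensitivity, which protocol 4.1 calls an important identified risk. There would also be none for malignancy or GI perforation, which it names as potential risks.

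Grouped counts matter more than usual here. SAP Table 1 gives estimated arm sizes of 28, 14, 14 and 27 (total 83), and all efficacy results are descriptive. The safety description is therefore one of the main things the trial can still contribute. A reader of the report would also not learn that the AESI output departs from protocol 11.4.3.1, because SAP 1.6 does not mention it.

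**Working it through.** No power or error-rate figure is involved. The check sets three lists side by side: protocol 11.4.3.1, protocol 10.5.1.3 and SAP Table 5.

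| Protocol 11.4.3.1 category | In SAP Table 5 | Separate laboratory analysis in SAP 2.4.5.3 |
|---|---|---|
| Neutropenia | Only if it leads to permanent discontinuation | Yes: maximal grade, time to Grade 3 or 4 |
| Thrombocytopenia | Only if it leads to permanent discontinuation | Yes: grade, time to below 100 Giga/L |
| Infections | Only clinically significant ones | No |
| Hepatic disorders | ALT of at least 3 x ULN, or ALT rise leading to permanent discontinuation | Yes: PCSA, time to onset, ALT against bilirubin plot |
| Diverticulitis, GI ulceration, perforation | No row | No |
| Lipid elevation | No row | Yes: PCSA, time to LDL and cholesterol thresholds |
| Systemic allergic reactions | No row | No |
| Malignancy | No row | No |
| Lupus-like syndrome | No row | No |
| Demyelinating disorders | No row | No |

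**Counts.** Six of ten categories have no row, and 10 - 6 = 4 are present in narrower form. None of the ten has a MedDRA search in Table 5. Of the six absent categories, one (lipids) has a laboratory analysis, so 6 - 1 = 5 are without one. Against protocol 10.5.1.3, Table 5 omits nothing.

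**Could the tick-box reach the absent categories?** Protocol 10.5.1.3 does not list them, so the protocol gives sites no instruction to classify them as AESIs. For one of them it says "Confirmed diverticulitis or gastrointestinal ulceration should be reported as AEs" (10.7.6). SAP 2.1.4 describes AESIs with open-ended wording, but no criterion in Table 5 goes beyond the 10.5.1.3 list.

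**What narrowing does.** Under protocol 10.4.1, neutrophils from 500 to below 1000/mm³ without signs of infection lead to a temporary hold. If that resolves and treatment resumes, the event stays out of the AESI tables. It still appears as Grade 3 in the SAP neutropenia summary.

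**Where the events do appear.** SAP 2.4.5.1 tabulates all TEAEs, SAEs and TEAEs leading to discontinuation by SOC, HLGT, HLT and PT, and by SOC alone. What these tables cannot give is a patient count for a risk whose terms fall under more than one grouping. A patient with two relevant terms is counted in both rows, so the rows cannot be added. A SOC row also mixes the risk with unrelated events. One patient is 1/14 = 7.1% of a 14-patient arm and 1/28 = 3.6% of a 28-patient arm, so counting a patient once or twice is visible.

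**Was the change declared or forced?** SAP 1.6 lists the changes from the protocol's analysis plan, and this is not among them. The data loss it cites concerns efficacy, ADA and biomarker assessments. All AEs are still coded in MedDRA (SAP 2.1.4.1).

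**Related gap.** Protocol 11.4.3.2.2 plans the incidence of liver-related AEs using the hepatic disorder SMQ. The hepatic part of SAP 2.4.5.3 holds only laboratory displays.

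**The case against.** The best defence is that Table 5 is faithful to the protocol. Section 10.5.1.3 is where the protocol defines AESIs, it says the list changes only by amendment, and Table 5 reproduces it in full. That stands. The root of the problem is that the protocol uses one term for two lists. It does not settle the matter, because 11.4.3.1 is the analysis section and assigned the coding of its categories to the SAP.

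The second defence is that the named risks reach other focused tables. This also stands in large part. GI perforation and anaphylaxis must be reported as SAEs (protocol 10.7.6, 10.7.5). Cancers diagnosed during the study are on the medically important list in 10.5.1.2. Systemic hypersensitivity and severe demyelinating disease are criteria for permanent discontinuation (10.4.3), so they enter the discontinuation tables.

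These facts rule out several stronger readings that a reader might infer:

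- **That the trial could not detect these risks, or that neutropenia managed by a hold goes unreported.** The TEAE, SAE and laboratory outputs cover them.
- **That an empty AESI row would pass for an absence of signal.** The six categories have no row, so there is nothing to misread in that way.
- **That the events survive only as isolated preferred terms.** SOC, HLGT and HLT levels are planned.
- **That a row for major cardiovascular events is also owed.** Protocol 4.1 names that risk, but 11.4.3.1 does not list it, so its absence is not a departure.
- **That sites were never told to tick the box for these events.** CRF completion guidance is not among the documents; only the protocol's silence can be shown.

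**Conclusion.** The point holds as an unreconciled protocol conflict that the SAP resolved silently in favour of the reporting list. Followed as written, the SAP omits an analysis specified in protocol 11.4.3.1: six of ten categories absent, four narrowed, and no MedDRA search for any in Table 5. Of the three important identified risks in protocol 4.1, hypersensitivity has no row, neutropenia is cut to events causing permanent discontinuation, and infections are kept in the clinically significant form.

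The loss is one of display: a pooled patient-level count per named risk, mainly for hypersensitivity, GI events, malignancy, lupus-like syndrome and demyelination. It should be corrected, but it does not threaten the safety data.

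This rests on two assumptions. The AESI displays use only the Table 5 criteria, as SAP 2.4.5.1 says. No separate document supplies the missing searches; the SAP cites none.

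**What to change.** In SAP Table 5, add a second block that applies MedDRA searches to all coded TEAEs for the ten categories of protocol 11.4.3.1, with the query or term list stated for each. For hepatic disorders, the SMQ already named in protocol 11.4.3.2.2 can serve. Keep the box-ticked events of 10.5.1.3 as their own block, so that reporting definitions do not change. Run the AESI displays of SAP 2.4.5.1 on both blocks. In SAP 1.6, state that the protocol holds two lists and how they are reconciled. If the sponsor prefers not to add the searches, the reduction should at least be declared and justified there.

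The cost is SAP wording and a modest amount of query programming. AEs are already coded, so no new data collection is needed.
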